13.5 Stopping Rules

13.5.1 As described above, the study will use a standard 3+3 dose escalation design. For each three patient cohort, DLT will be assessed as above. In the case of 2/3 DLTs, the trial will be terminated with the previous level being the MTD. In the case of 1/3 DLTs, an additional three patients will be enrolled at the current dose level. In the event of a total

of 2 or more DLTs in 6 patients, the trial will be terminated with the previous dose level being the MTD.

- (Y)** 1. Does the patient have a pathologically-confirmed diagnosis of renal cell carcinoma?
- (Y)** 2. Has the patient been deemed medically inoperable by his/her urologist?
- (Y)** 3. Is the tumor greater than 4 cm in greatest dimension per imaging?
- (Y)** 4. Is the patient over the age of 18?
- (Y)** 5. Has the patient provided written informed consent for study participation?
- (Y)** 6. Has the patient undergone complete pre-treatment work-up as listed in the protocol document (section 6.3)?
- (N)** 7. Does the patient have a history of any prior invasive cancer in the last 5 years (except for a diagnosis of low-risk prostate cancer post appropriate therapy, treated non-melanoma/melanoma skin cancer, appropriately treated ductal carcinoma in situ or early stage invasive carcinoma of breast and appropriately treated in-situ or early stage cervical/endometrial cancer), OR any prior radiation therapy to the upper abdomen?
- (N)** 8. Is the patient a pregnant or nursing woman?
- (Y)** 9. If the patient is a woman of childbearing potential, are they agreeable to the use of contraceptive methods (hormonal or barrier method of birth control; abstinence) from the point of study entry and for the duration of completion of all active treatments? Should a woman become pregnant or suspect she is pregnant while participating in this study, is she willing to inform her treating physician immediately?
- (N)** 10. Has the patient received any treatment with a non-approved or investigational drug within 28 days of study treatment?
- (N)** 11. Is the patient's ECOG performance score < 2?
- (Y)** 12. Has the patient passed the MRI screening process?

The following questions will be asked at Study Registration:

-----**(Y)**. Has the Eligibility Checklist (*above*) been completed? Is the patient eligible for this study?

-----Date the study-specific Consent signed

-----Patient's Name^[1]_[SEP]

-----Patient's UWHC MRN

----- Patient's Date of Birth

----- Patient's zip code

The Eligibility Checklist will be completed in its entirety prior to enrollment on study. The completed, signed, and dated Checklist used at study entry must be retained in the patient's study file.

Completed by _____

Date _____

Verified by _____

Date _____

UWCCC Data Safety Monitoring Plan

Oversight And Monitoring Plan

The UWCCC Data and Safety Monitoring Committee (DSMC) is responsible for the regular review and monitoring of all ongoing clinical research in the UWCCC. A summary of DSMC activities are as follows:

- Reviews all clinical trials conducted at the UWCCC for subject safety, protocol compliance, and data integrity.
- Reviews all Serious Adverse Events (SAE) requiring expedited reporting, as defined in the protocol, for all clinical trials conducted at the UWCCC, and studies conducted at external sites for which UWCCC acts as an oversight body.
- Reviews all reports generated through the UWCCC DSMS elements (Internal Audits, Quality Assurance Reviews, Response Reviews, Compliance Reviews, and Protocol Summary Reports) described in Section II of this document.
- Notifies the protocol Principal Investigator of DSMC decisions and, if applicable, any requirements for corrective action related to data or safety issues.
- Notifies the CRC of DSMC decisions and any correspondence from the DSMC to the protocol Principal Investigator.
- Works in conjunction with the UW Health Sciences IRB in the review of relevant safety information as well as protocol deviations, non-compliance, and unanticipated problems reported by the UWCCC research staff.
- Ensures that notification is of SAEs requiring expedited reporting is provided to external sites participating in multi-institutional clinical trials coordinated by the UWCCC.

Monitoring And Reporting Guidelines

UWCCC quality assurance and monitoring activities are determined by study sponsorship and risk level of the protocol as determined by the PRMC. All protocols (including Intervention Trials, Non-Intervention Trials, Behavioral and Nutritional Studies, and trials conducted under a Training Grant) are evaluated by the PRMC at the time of committee review. UWCC monitoring requirements for trials without an acceptable external DSMB are as follows:

Intermediate Monitoring

Protocols subject to intermediate monitoring generally include UW Institutional Phase I/II and Phase II Trials. These protocols undergo review of subject safety at regularly scheduled DOWG meetings where the results of each subject's treatment are discussed and the discussion is documented in the DOWG meeting minutes. The discussion includes the number of subjects enrolled, significant toxicities, dose adjustments, and responses observed. Protocol Summary Reports are submitted on a semi-annual basis by the study team for review by the DSMC.

Review and Oversight Requirements

Serious Adverse Events requiring reporting within 24 hours (as described in the protocol) must also be reported to the Data and Safety Monitoring Committee (DSMC) Chair via an email to [contact] within one business day. The OnCore SAE Details Report must be submitted along with other report materials as appropriate (NCI AdEERS form or FDA Medwatch Form #3500 and/or any other documentation available at that time of initial reporting). The DSMC Chair will review the information and determine if immediate action is required. Within 10 working days, all available

subsequent SAE documentation must be submitted electronically along with a 24 hour follow-up SAE Details Report and a completed UWCCC SAE Routing Form to [contact]. All information is entered and tracked in the UWCCC database.

The Principal Investigator notifies all investigators involved with the study at the UWCCC, the IRB, the sponsor, and the funding agency and provides documentation of these notifications to the DSMC.

If the SAE occurs on a clinical trial in which the UW PI serves as the sponsor-investigator, the PI reviews the event to determine whether the SAE requires reporting to the FDA and other participating investigators.

For a multiple-institutional clinical trial the PI is responsible for ensuring SAEs are reported to the FDA as well as to all participating investigators

Serious Adverse Event-Reported within 10 Days

Serious Adverse Events requiring reporting within 10 days (as described in the protocol) must also be reported to the Data and Safety Monitoring Committee (DSMC) Chair via an email to [contact]. The OnCore SAE Details Report must be submitted along with other report materials as appropriate (NCI AdEERS form or FDA Medwatch Form #3500 and/or any other documentation available at that time of initial reporting). The DSMC Chair will review the information and determine if further action is required. All information is entered and tracked in the UWCCC database.

The Principal Investigator notifies all investigators involved with the study at the UWCCC, the IRB, the sponsor, and the funding agency and provides documentation of these notifications to the DSMC.

If the SAE occurs on a clinical trial in which the UW PI serves as the sponsor-investigator, the PI reviews the event to determine whether the SAE requires reporting to the FDA and other participating investigators.

For a multiple-institutional clinical trial the PI is responsible for ensuring SAEs are reported to the FDA as well as to all participating investigators.

Sponsor-Investigator Responsibilities for SAE Review

In the event the UWCCC Principal Investigator is acting as the Sponsor-Investigator (i.e., the PI holds the IND), the PI assumes responsibilities of the study sponsor in accordance with FDA 21 CFR 312.32. In this capacity, the UWCCC PI reviews all reports of serious adverse events occurring on the study at the UWCCC and participating external sites and makes a determination of 1) **suspectedness** (i.e., whether there is a reasonable possibility

That the drug caused the AE); and 2) unexpectedness in the context of this study. SAE with suspected causality to study intervention deemed unexpected are reported as IND safety Reports by the UWCCC PI to the FDA, all participating investigators on the study, within 15 calendar days. All fatal or life-threatening SAE that are unexpected and have suspected causality to the study intervention will be reported by the UWCCC PI to the FDA, all participating investigators on the study within 7 calendar days.

Study Progress Review

Protocol Summary Reports (PSR) are required to be submitted to the DSMC in the timeframe determined by the risk level of the study (quarterly; semi-annually; or annually). The PSR provides a cumulative report of SAEs, as well as instances of non-compliance, protocol deviations, and unanticipated problems, toxicities and responses that have occurred on the protocol in the timeframe specified. PSRs for those protocols scheduled for review are reviewed at each DSMC meeting.

Protocol Summary Reports enable DSMC committee members to assess whether significant benefits or risks are occurring that would warrant study suspension or closure. This information is evaluated by the DSMC in conjunction with other reports of quality assurance activities (e.g., reports from Internal Audits, Quality Assurance Reviews, etc.) occurring since the prior review of the protocol by the DSMC. Additionally, the DSMC requires the study team to submit external DSMB or DSMC reports, external monitoring findings for industry-sponsored studies, and any other pertinent study-related information.

In the event that there is significant risk warranting study suspension or closure, the DSMC will notify the PI of the DSMC findings and ensure the appropriate action is taken for the protocol (e.g., suspension or closure). The DSMC ensures that the PI reports any temporary or permanent suspension of a clinical trial to the sponsor (e.g., NCI Program Director, Industry Sponsor Medical Monitor, Cooperative Group Study Chair, etc.) and other appropriate agencies. DSMC findings and requirements for follow-up action are submitted to the CRC

EXPEDITED REPORTING OF SERIOUS ADVERSE EVENTS

Depending on the nature, severity, and attribution of the serious adverse event an SAE report will be phoned in, submitted in writing, or both according to Table below. All serious adverse events must also be reported to the UWCCC Data and Safety Monitoring Committee Chair. All serious adverse events must also be reported to the UW IRB (if applicable), and any sponsor/funding agency not already included in the list.

Determine the reporting time line for the SAE in question by using the following table. Then refer to sections A and B below if the SAE occurred at the UWCCC or sections C and D if the SAE occurred at 1 South Park, Johnson Creek, or a WON Site.

SAE Requiring [24] Hour Reporting Occurs at UWCCC:

1. Report to the UWCCC:

Reference the **SAE SOP** (Standard Operating Procedure) and the **SAE Reporting Workflow for DOWGs** on the UWCCC website (<http://www.uwccc.wisc.edu>) for specific instructions on how and what to report to the UWCCC for [24] hour initial and follow-up reports. **A follow-up report is required to be submitted within 5 days of the initial [24] hour report.**

For this protocol, the following UWCCC entities are required to be notified:

- a) [contact]
- b) *[name], UWCCC PI*
- c) *[name], UWCCC Radiotherapy PM*
- d) Any other appropriate parties listed on the SAE Routing Form (for follow-up reports only)

2. Report to the IRB:

Consult the UW-IRB website for reporting guidelines

SAE Requiring [10] Day Reporting Occurs at UWCCC:

1. Report to the UWCCC:

Reference the **SAE SOP** and the **SAE Reporting Workflow for DOWGs** on the UWCCC website (<http://www.uwccc.wisc.edu>) for specific instructions on how and what to report to the UWCCC for [10] day reports.

For this protocol, the following entities are required to be notified:

- a) [contact]
- b) Any appropriate parties listed on SAE Routing Form

2. Report to the IRB:

Consult the UW-IRB website for reporting guidelines.

Other Reporting Requirements

Reporting to the FDA

Serious Adverse Events occurring on studies on which a UW PI is acting as sponsor-investigator must be reported to the FDA within the appropriate time frame. Mandatory and voluntary reporting guidelines and instructions are outlined on the FDA website:

<http://www.fda.gov/Safety/MedWatch/HowToReport/default.htm>

Expedited reporting requirements for adverse events that occur within 30 days of the last dose of radiation therapy¹

FDA Reporting Requirements for Serious Adverse Events (21 CFR Part 312)			

NOTE: Investigators MUST immediately report to the PI, UWCCC and UW IRB per policy ANY Serious Adverse Events, whether or not they are considered related to the investigational agent(s)/intervention (21 CFR 312.64). FDA Med Watch (3500A) will be submitted for grade 4 and 5 events at the discretion of the sponsor-investigator.
 
An adverse event is considered serious if it results in ANY of the following outcomes:
 
 7) Death. 8) A life-threatening adverse event. 9) An adverse event that results in inpatient hospitalization or prolongation of existing hospitalization for ≥ 24 hours. 10) A persistent or significant incapacity or substantial disruption of the ability to conduct normal life functions. 11) A congenital anomaly/birth defect. 12) Important Medical Events (IME) that may not result in death, be life threatening, or require hospitalization may be considered serious when, based upon medical judgment, they may jeopardize the patient or subject and may require medical or surgical intervention to prevent one of the outcomes listed in this definition (FDA, 21 CFR 312.32; ICH E2A and ICH E6). 			

ALL SERIOUS adverse events that meet the above criteria* MUST be immediately reported to the UWCCC within the timeframes detailed in the table below: With the exception of a 24 hr hospitalization for MWA procedure
			
Hospitalization	Grade 1 and Grade 2 Timeframes	Grade 3 Time Frames	Grade 4 & 5 Timeframes
Resulting in hospitalization ≥ 24 hrs	Not required	10 Calendar Days	24 Hour; 5 Calendar Days
Not resulting in Hospitalization ≥ 24 hrs	Not required	10 Calendar Days	

 • See section 13.0 for listing of toxicities • Grade 3 toxicities during the 24hr hospitalization for MWA are exemption from SAE reporting 
Expedited AE reporting timelines are defined as:
 
 • 24-Hour; 5 Calendar Days – The AE must initially be reported within 24 hours of learning of the AE, followed by a complete expedited report within 3 calendar days of the initial 24-hour report. • 10 Calendar Days – A complete expedited report on the AE must be submitted within 5 calendar days of learning of the AE 			

¹ Serious adverse events that occur more than 30 days after the last administration of investigational intervention and have an attribution of possible, probable, or definite require reporting as follows:
 
Expedited 24-hour notification followed by complete report within 10 working days for:
 
 • All Grade 4, and 5 AEs

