 - 4.1.1 Patients with imaging findings consistent with renal cell carcinoma
 - 4.1.2 Deemed medically inoperable per urology evaluation
 - 4.1.3 Tumor size > 4cm in largest dimension

- 4.1.4 ECOG performance status of < 2
- 4.1.5 Age > 18 years
- 4.1.6 Signed informed consent document(s)
- 4.1.7 Patients with metastatic disease will not be excluded

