4.2 Exclusion Criteria

- 4.2.1 Patients who fail MRI screening
- 4.2.2 Pregnant or nursing women
- 4.2.3 History of prior radiation therapy to the upper abdomen
- 4.2.4 History of invasive cancer in the last 3 years (except for appropriately treated low-risk prostate cancer, treated non-melanoma/melanoma skin cancer, appropriately treated ductal carcinoma in situ or early stage invasive carcinoma of breast and appropriately treated in-situ/early stage cervical/endometrial cancer)
- 4.2.5 Treatment with a non-approved or investigational drug within 28 days of study treatment

5. Registration Procedures

Patients may not begin protocol treatment prior to registration. All patients must meet eligibility criteria listed in Section 4 and provide written informed consent. The study coordinator will verify eligibility, assign a case number, and register the patient in the UWCCC ONCORE database prior to study treatment. The following information will be recorded:

- 5.1 Protocol number
- 5.2 Patient's name and initials
- 5.3 Patient's medical record number
- 5.4 Patient demographic data including gender, birth date, race and zip code.
- 5.5 Signed patient consent form dates
- 5.6 Attending physician
- 5.7 HIPAA authorization form dates

[figure not shown]
6. Treatment Plan/Overview

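### Eligibility checklist item 11 reverses the ECOG criterion of Section 4, and the checklist and Section 4 also differ on the prior-cancer look-back and on proof of diagnosis

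*Combined protocol and SAP*

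**What the plan says.** **ECOG.** The synopsis and Section 4.1.4 both list "ECOG performance status of < 2" as an inclusion criterion. Item 11 of the Eligibility Checklist (Appendix 1) reads "N) 11. Is the patient's ECOG performance score < 2", so the answer printed on the form is N.

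**Prior cancer.** Section 4.2.4 excludes patients on the basis of "History of invasive cancer in the last 3 years", with listed exceptions. Checklist item 7 asks about a "history of any prior invasive cancer in the last 5 years", with essentially the same exceptions.

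**Diagnosis.** Section 4.1.1 admits "Patients with imaging findings consistent with renal cell carcinoma". The synopsis requires histological confirmation and checklist item 1 requires pathological confirmation.

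**Status of the two sources.** Section 5 states: "All patients must meet eligibility criteria listed in Section 4 and provide written informed consent". Appendix 1 requires the checklist to be finished before enrolment, provides lines for the person completing it and the person verifying it, and adds: "The completed, signed, and dated Checklist used at study entry must be retained in the patient's study file". The question asked at registration, "Is the patient eligible for this study", is printed with Y.

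**The concern.** Two parts of the protocol govern entry, and they do not describe the same patients. On ECOG they point in opposite directions: someone who satisfies 4.1.4 cannot give the printed answer to item 11 truthfully. On the look-back and the diagnosis they overlap but are not identical.

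What is at stake is the record that each patient was eligible. If staff follow Section 4 as printed, the true answer to item 11 is yes for every enrolled patient, against a printed N. Each retained form then carries either an apparent eligibility deviation or a wrong answer. On the other two points, a patient can be eligible by Section 4 and ineligible by the signed form.

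**Working it through.** There is no design figure to reproduce. The check compares the texts and then tests whether a lost underline in the PDF text could explain the ECOG conflict.

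**Step 1: what the printed letters mean.** The appendix gives no legend, so the convention is inferred.

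- Y is printed on items 1 to 6, 9 and 12 (8 items). Apart from item 6 (work-up complete) and item 9 (contraception), these correspond to entry conditions in Section 4.
- N is printed on items 7, 8, 10 and 11 (4 items). Items 7, 8 and 10 correspond to exclusions in Section 4.2.
- Leaving item 11 aside, 11 of 11 items fit the reading that the printed letter is the qualifying answer. Items 6 and 9 have no counterpart in Section 4, and item 9 applies only to women of childbearing potential. Dropping both leaves 9 of 9.
- The registration question on eligibility is printed Y, which fits the same reading.

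**Step 2: ECOG under every combination of signs.** Take grades 0 to 4. Item 11 is passed when the answer is no. Allow < or ≤ separately in each place.

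| Section 4 and synopsis | Item 11 | Meet Section 4 | Pass item 11 | Satisfy both |
|---|---|---|---|---|
| < 2 | < 2 | 0, 1 | 2, 3, 4 | none |
| < 2 | ≤ 2 | 0, 1 | 3, 4 | none |
| ≤ 2 | < 2 | 0, 1, 2 | 2, 3, 4 | 2 |
| ≤ 2 | ≤ 2 | 0, 1, 2 | 3, 4 | none |

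Grades 0 and 1 meet Section 4 and fail item 11 in all four rows. Grades 3 and 4 pass item 11 and fail Section 4 in all four rows. Only grade 2 depends on the reading, and it satisfies both rules in one row of four.

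**Step 3: look-back.** The rules differ over a band of 5 − 3 = 2 years. A patient whose non-exempt invasive cancer falls 3 to 5 years back is not excluded by 4.2.4 but fails item 7. Anyone who passes the 5-year rule also passes the 3-year rule, so the checklist is the narrower of the two.

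**Step 4: diagnosis.** A patient with imaging findings only meets 4.1.1 but fails item 1 until the biopsy is read. Section 6.1 places the biopsy before SBRT. Section 6.6 and footnote 3 of Table 2 allow the diagnostic biopsy to come after consent. This sequence may explain the wording of 4.1.1, but 4.1.1 is written as an inclusion criterion with no reference to timing, and it disagrees with the synopsis as well as with item 1. Here too the checklist is the narrower rule.

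**The case against.** The strongest reply is that item 11 is a visible slip with little consequence. Section 5 names Section 4 as the standard, the synopsis agrees with it on ECOG, and the coordinator verifies eligibility. An item that would fail every patient who meets Section 4 should be noticed at the first registration. No one with ECOG 3 or 4 could properly be enrolled on the strength of item 11, because that patient fails 4.1.4. ECOG is also assessed before treatment (Table 2) and collected at baseline (Section 11.0), so a wrong checklist answer can be checked against other data. Most of this stands, and it is why no effect on the MTD or on local control is claimed. It does not remove the need for correction: staff would have to override the signed form for every patient.

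A second reply is that the Y/N convention is inferred and that a misread sign other than a lost underline is possible. If the published page shows ≥ in item 11, the ECOG conflict disappears. That cannot be strictly excluded from the text, but ≥ is preserved in the hospitalization criteria of Table 3, and nothing suggests it was lost here.

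Third, the diagnosis difference is largely explained by the biopsy sequence, and the stricter look-back on the form admits no one whom 4.2.4 excludes. Both statements are right. They make these two points lesser ones, but the texts still disagree. Nor is the 3- versus 5-year difference an evident misprint: nothing in the documents shows which is meant.

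**Conclusion.** The concern holds. As printed, item 11 reverses the ECOG criterion, and the reversal covers grades 0, 1, 3 and 4 whichever of < or ≤ was intended in either place. Either the letter or the comparison sign in item 11 is wrong. The look-back differs over a 2-year band, and the diagnosis requirement differs between 4.1.1 on one side and the synopsis and item 1 on the other. No passage reconciles any of the three.

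The ECOG conclusion rests on two assumptions: that the printed letter is the qualifying answer, which all other items support, and that the direction of the sign in item 11 is as it appears. The documents give no frequencies for ECOG grades or for prior cancers 3 to 5 years back, so the number of patients affected by the lesser differences is not estimated. For item 11 the exposure is the checklist of every enrolled patient, 18 + 10 = 28 at the planned maximum. The consequence is a defective eligibility record. It should be fixed, but it does not threaten the dose-escalation result.

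**What to change.** 1. Change item 11, either its printed answer or its comparison sign, so that it agrees with 4.1.4 and the synopsis.
2. Have the sponsor reconcile the look-back period in 4.2.4 and item 7, and state it identically in both places.
3. Have the sponsor reconcile the diagnosis requirement across the synopsis, 4.1.1 and item 1. If the intention is consent on imaging findings with biopsy confirmation before registration, say so in 4.1.1.
4. Add a one-line legend to the checklist stating that the printed letter is the answer required for eligibility, if that is the convention.

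The cost is a wording amendment to Appendix 1 and, depending on how points 2 and 3 are settled, to Section 4 or the synopsis. No new procedure, visit or data item is needed.
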